1.2. Name and description (characteristics) of the test drug

1.2.1. Test drug

Trade name: not applicable. Product code: BCD-089.

National nonproprietary name: Anti-interleukin-6 receptor monoclonal antibody

Pharmaceutical form: solution for injection.

Composition per 1 mL:

Active substance: [REDACTED]

Excipients:

[REDACTED]

Manufacturer: JSC BIOCAD, Russia

Shelf life: 2 years.

Storage and transportation conditions:

[REDACTED]

Packaging:

[REDACTED]

Labeling:

In accordance with Article 46 of Federal Law “On the Circulation of Medicinal Products” No. 61-Φ3 of April 12, 2010, the primary packaging of the test drug contains the following Russian text in easily readable font:

Translated from Russian to English, dated 06-Jul-2020

[REDACTED]

[REDACTED]

Manufacturer: JSC BIOCAD, Russia

Shelf life: 2 years.

Storage and transportation conditions:

[REDACTED]

[REDACTED]

Packaging:

[REDACTED]

[REDACTED]

[REDACTED]

Labeling:

In accordance with Article 46 of Federal Law “On the Circulation of Medicinal Products” No. 61-Φ3 of April 12, 2010, the primary packaging of the test drug contains the following Russian text in easily readable font:

- “Diluent”,
- batch number,
- release date,
- expiry date,
- volume.

The secondary packaging contains the following information in Russian in easily readable font:

- name: “Diluent”,
- manufacturer name: JSC BIOCAD, Russia,
- batch number,
- release date,
- expiry date,
- method of administration,
- volume,
- storage conditions,

Translated from Russian to English, dated 06-Jul-2020

- cautionary information.

Primary and secondary packaging of the test drug will be additionally labeled with: “For clinical studies only”.

Method of administration and dosing regimen:

In this study, the drug will be administered as a single-dose subcutaneously. The administered dose of BCD-089 depends on the cohort into which the volunteer was assigned:

1. Cohort 01 - 1 volunteer to whom a single subcutaneous injection of BCD-089 at a dose of 0.06 mg/kg will be administered.
2. Cohort 02 - a maximum of 6 volunteers to whom a single subcutaneous injection of BCD-089 at a dose of 0.3 mg/kg will be administered.
3. Cohort 03 - a maximum of 6 volunteers to whom a single subcutaneous injection of BCD-089 at a dose of 0.625 mg/kg will be administered.
4. Cohort 04 - a maximum of 6 volunteers to whom a single subcutaneous injection of BCD-089 at a dose of 1.0 mg/kg will be administered.
5. Cohort 05 - a maximum of 6 volunteers to whom a single subcutaneous injection of BCD-089 at a dose of 1.6 mg/kg will be administered.
6. Cohort 06 - a maximum of 6 volunteers to whom a single subcutaneous injection of BCD-089 at a dose of 2.2 mg/kg will be administered.
7. Cohort 07 - a maximum of 6 volunteers to whom a single subcutaneous injection of BCD-089 at a dose of 2.9 mg/kg will be administered.

Method of administration:

Dose calculation:

The dose is calculated in mg/kg of the volunteer's body weight. Based on the dose assigned according to the study design, the dose is calculated per 1 administration of the drug.

The total dose per 1 administration (mg) is equal to the weight of the volunteer (kg) multiplied by the dose specified for the cohort, which the volunteer is assigned to (mg/kg). A detailed table with the calculation of drug doses based on the volunteer body weight is provided to the Investigator.

Instructions for preparing the solutions for cohorts

Preparation of the solution for injection should be prepared using aseptic technique.

Translated from Russian to English, dated 06-Jul-2020

[Redacted content]

Translated from Russian to English, dated 06-Jul-2020

[REDACTED]

1.3. Summary of potentially clinically relevant results of preclinical studies, as well as results of clinical studies that are relevant for this study

1.3.1. Non-clinical studies of the test drug

[REDACTED]

1.3.1.1. Summary of physicochemical studies

[REDACTED]

Translated from Russian to English, dated 06-Jul-2020

[REDACTED]

1.3.1.2. Preclinical studies in laboratory animals

1.3.1.2.1. A study of the potency of BCD-089 in a model of collagen-induced arthritis

[REDACTED]

Translated from Russian to English, dated 06-Jul-2020

[Redacted content]

Translated from Russian to English, dated 06-Jul-2020

[Redacted content]

Translated from Russian to English, dated 06-Jul-2020

1.3.1.2.2. BCD-089 pharmacokinetic study following a single-dose administration to monkeys

[Redacted text block containing multiple lines of blacked-out content]

Translated from Russian to English, dated 06-Jul-2020

[REDACTED]

1.3.1.2.3. BCD-089 pharmacokinetic study following repeated-dose administration to monkeys

[REDACTED]

[REDACTED]

[REDACTED]

Translated from Russian to English, dated 06-Jul-2020

[Redacted text block]

1.3.1.2.4. Study of BCD-089 immunogenicity following repeated-dose administration

[Redacted text block]

Translated from Russian to English, dated 06-Jul-2020

[REDACTED]

1.3.1.2.5. Acute toxicity study of BCD-089

[REDACTED]

1.3.1.2.6. BCD-089 repeated-dose toxicity study

[REDACTED]

Translated from Russian to English, dated 06-Jul-2020

[REDACTED]

1.3.1.2.7. Evaluation of local tolerance of BCD-089 in a toxicity study with repeated-dose administration of the drug

[REDACTED]

Translated from Russian to English, dated 06-Jul-2020

[Redacted text block]

1.3.1.2.8. BCD-089 cross-reactivity evaluation

[Redacted text block]

Translated from Russian to English, dated 06-Jul-2020

1.3.1.2.9. Preclinical study of cytokine storm

[REDACTED]

1.3.2. Clinical studies of the test drug

Not performed.

1.4. Summary of known and potential risks and benefits for clinical trial subjects (risk/benefit ratio)

Benefit evaluation

BCD-089 is an innovative drug, which has never been used in humans. The first stage of BCD-089 clinical development will be to evaluate its effects in healthy volunteers, which means that participants in such a study will not derive subjective (personal) benefits from their participation in it, except for a detailed medical examination; however, data obtained after the completion of this study will have high scientific value and may help introduce into clinical practice a new highly effective product for the treatment of severe autoimmune disorders.

Risk evaluation

[REDACTED]

Translated from Russian to English, dated 06-Jul-2020

[Redacted content]

Translated from Russian to English, dated 06-Jul-2020

[Redacted content]

Translated from Russian to English, dated 06-Jul-2020

1.5. Description and justification of the study design, the method of administration of the test drug, dose, dosing regimen and the course of treatment

1.5.1. Description and justification of the study design

Clinical study No. BCD-089-1 is a classic open-label, single-center, non-randomized cohort clinical study of the pharmacokinetics, pharmacodynamics, tolerability and safety of a novel drug in healthy volunteers at increasing doses (phase 1, 3+3 design).

Study No. BCD-089-1 includes seven cohorts:

1. Cohort 01 - 1 volunteer to whom a single subcutaneous injection of BCD-089 at a dose of 0.06 mg/kg will be administered.
2. Cohort 02 - a maximum of 6 volunteers to whom a single subcutaneous injection of BCD-089 at a dose of 0.3 mg/kg will be administered.
3. Cohort 03 - a maximum of 6 volunteers to whom a single subcutaneous injection of BCD-089 at a dose of 0.625 mg/kg will be administered.
4. Cohort 04 - a maximum of 6 volunteers to whom a single subcutaneous injection of BCD-089 at a dose of 1.0 mg/kg will be administered.
5. Cohort 05 - a maximum of 6 volunteers to whom a single subcutaneous injection of BCD-089 at a dose of 1.6 mg/kg will be administered.
6. Cohort 06 - a maximum of 6 volunteers to whom a single subcutaneous injection of BCD-089 at a dose of 2.2 mg/kg will be administered.
7. Cohort 07 - a maximum of 6 volunteers to whom a single subcutaneous injection of BCD-089 at a dose of 2.9 mg/kg will be administered.

The inclusion of volunteers in the study is sequential. The first to participate in the study is one volunteer, representing the cohort “01”, who is administered a single subcutaneous injection of BCD-089 0.06 mg/kg. In the absence of grade 3-4 adverse events related to the test product, developing within the first 7 days after the injection, three volunteers are included in cohort 02, who will receive the estimated minimum single starting dose.

The doses for each cohort were calculated using a modified Fibonacci sequence.

According to the “3+3” principle, enrollment to the study is sequential. First, one volunteer is included in the first cohort. In the absence of grade 3-4 adverse events related to the test product,

Translated from Russian to English, dated 06-Jul-2020

developing within the first 7 days after the injection, three volunteers are included in cohort 02. Further, the volunteer inclusion algorithm corresponds to the following general principle:

- a) In the absence of any grade 3-4 AEs (DLT) associated with the test product within 7 days after the injection, the next cohort of three volunteers with dose escalation is included in the study - cohort 02 (cohort 03, cohort 04, etc.).
- b) If grade 3-4 AEs (DLT) associated with the test product are recorded in only one volunteer in a cohort of three volunteers, three more healthy volunteers are additionally included in this cohort.
- c) With the development of grade 3-4 AEs (DLT) associated with the test product in two of six volunteers, the dose at which this event was recorded will be taken as the maximum tolerated dose, further dose escalation will be ceased.

Thus, dose limiting toxicity will be assessed close to the time of administration, during the first seven days after the injection. However, it is not the end of the volunteers follow-up - monitoring of their condition, as well as blood sampling for the study of pharmacokinetics, pharmacodynamics, and safety, will be carried out up to 71 days from the moment of injection - the selected duration of the study is sufficient for a full study of pharmacokinetics, pharmacodynamics and safety following a single-dose administration.

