	
Further, the volunteer inclusion algorithm corresponds to the following general principle:
 
In the absence of any grade 3-4 AEs (DLT) associated with the test product within 7 days after the injection, the next cohort of three volunteers with dose escalation will be included in the study - Cohort 03 (cohort 04, cohort 05, cohort 06, cohort 07).
 
If grade 3-4 AEs (DLT) associated with the test product were recorded in only one volunteer in a cohort of three volunteers, three more healthy volunteers will be additionally included in this cohort.
 
With the development of grade 3-4 AEs (DLT) associated with the test product in two of six volunteers, the dose at which this event was recorded will be taken as the maximum tolerated dose, further dose escalation will be ceased.
 
Thus, dose limiting toxicity will be assessed close to the time of administration, during the first seven days after the injection. However, it is not the end of the volunteers follow-up - monitoring of their condition, as well as blood sampling for the study of pharmacokinetics, pharmacodynamics, immunogenicity and safety, will be carried out up to 71 days from the moment of injection.
 
A 14-day screening examination and 13 subsequent visits are planned to be conducted during the study. The duration of the active phase of the study (from the moment of the drug injection to the final visit) is 71 days.
 
Due to the need for multiple blood sampling, the volunteer has to stay at the study site for the first day after the injection.

Test drug administration	
BCD-089 is administered according to the developed design:
 
1. Cohort 01 (sentinel patient) - 1 volunteer to whom a single subcutaneous injection of BCD-089 at a dose of 0.06 mg/kg will be administered.2. Cohort 02 - a maximum of 6 volunteers to whom a single subcutaneous injection of BCD-089 at a dose of 0.3 mg/kg will be administered.3. Cohort 03 - a maximum of 6 volunteers to whom a single subcutaneous injection of BCD-089 at a dose of 0.625 mg/kg will be administered.4. Cohort 04 - a maximum of 6 volunteers to whom a single subcutaneous injection of BCD-089 at a dose of 1.0 mg/kg will be administered.

Translated from Russian to English, dated 06-Jul-2020

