2.2. Study Objectives

1. To determine the safe dose range of BCD-089, which will subsequently be used in the phase II clinical study;
2. To determine the proportion of study participants in whom a single subcutaneous administration of BCD-089 was accompanied by the development of adverse events, including the proportion of volunteers with neutropenia of varying severity;

Translated from Russian to English, dated 06-Jul-2020

3. To determine the main pharmacokinetic parameters (AUC_{0-1680} , $AUC_{0-\infty}$, C_{max} , T_{max} , $T_{1/2}$, K_{el} and CL) of BCD-089 after a single subcutaneous injection in increasing doses to healthy volunteers;
4. To determine the main pharmacodynamic parameters (C_{max} , T_{max} , C_{min} , T_{min} , AUC_{0-1680}) for C-reactive protein, IL-6 and soluble receptor IL-6;
5. To determine the proportion of volunteers, in whom binding and/or neutralizing antibodies to BCD-089 were determined following its single administration.

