3. HYPOTHESES TESTED

The study is based on the hypothesis that the maximum tolerated dose of BCD-089 with a single-dose subcutaneous injection to healthy volunteers is 2.9 mg/kg of body weight.

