4.3.3. The inclusion of volunteers in the study, assignment of study numbers

Randomization is not used in this study.

Volunteers will be enrolled in the study sequentially according to the cohort principle, when the inclusion in each subsequent cohort is made after confirming the safety of the dose of BCD-089 used in the previous cohort (a detailed description is presented in Section “Design”).

[REDACTED]

The investigator records the screening number and study site number in the source documentation and CRF.

JSC BIOCAD maintains lists of screening and identification numbers of all volunteers enrolled in the study.

Translated from Russian to English, dated 06-Jul-2020

4.4. Description of doses and dosing regimens of the study drugs Description of the dosage form and labeling of the study drugs

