During the analysis, the list of methods used may be extended, if necessary for a high-quality data processing.

9.2. Rationale for the study sample size, including reasoning or calculations to support the statistical power and clinical validity of the study

The calculation of the study sample size was based on the "3 + 3" design and dose levels used in the study.

Volunteers cohort	Dose, mg/kg	Number of mandatory included volunteers	Number of volunteers that can be included in case of DLT development
01	0.06	1	0
02	0.3	3	3
03	0.625	3	3

Translated from Russian to English, dated 06-Jul-2020

Volunteers cohort	Dose, mg/kg	Number of mandatory included volunteers	Number of volunteers that can be included in case of DLT development
04	1.0	3	3
05	1.6	3	3
06	2.2	3	3
07	2.9	3	3

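### The escalation rule gives the name maximum tolerated dose to the dose whose toxicity stopped escalation, not to the highest dose cleared below it

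*Combined protocol and SAP*

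**What the plan says.** Section 1.5.1 sets three rules for cohorts of three. Rule (a) opens the next dose: "In the absence of any grade 3-4 AEs (DLT) associated with the test product within 7 days after the injection, the next cohort" is included. Rule (b) adds three volunteers when one of the first three has a dose-limiting toxicity (DLT). Rule (c) is the only readable rule that produces an MTD. Its trigger is "With the development of grade 3-4 AEs (DLT) associated with the test product in two of six volunteers", and its result is that "the dose at which this event was recorded will be taken as the maximum tolerated dose, further dose escalation will be ceased". The Synopsis (study design) and Sections 4.2, 4.4.1 and 6.1 carry the same rule.

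Four other places bear on it:

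- Section 4.3.3: "the inclusion in each subsequent cohort is made after confirming the safety of the dose of BCD-089 used in the previous cohort".
- Section 2.2, objective 1: "To determine the safe dose range of BCD-089, which will subsequently be used in the phase II clinical study".
- Section 3, on the study's hypothesis: "the maximum tolerated dose of BCD-089 with a single-dose subcutaneous injection to healthy volunteers is 2.9 mg/kg of body weight". This is the top planned dose.
- The sample size table in Section 9.2 gives cohorts 02 to 07 three mandatory volunteers each. The other three stand under the column "Number of volunteers that can be included in case of DLT development". Cohort 01 has one volunteer and no expansion.

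**The concern.** One event, two DLTs among six volunteers, both ends escalation and earns its dose the word tolerated. By the protocol's own condition for moving on, that dose was not confirmed safe. Where there is a highest dose that was confirmed safe, it is a lower one.

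Objective 1 asks for a safe dose range to carry into phase II, and rule (c) is the only readable rule that names a dose from the escalation result. A phase II planner could take the named dose as the top of the safe range when it is the first dose outside it.

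The same wording sits badly with Section 3. If an MTD can arise only through DLTs, the hypothesis that the MTD is 2.9 mg/kg can be supported only by toxicity at 2.9 mg/kg. A well-tolerated top dose would leave it undecided.

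**Working it through.** **Inputs.** Doses by cohort (Section 1.5.1): 0.06, 0.3, 0.625, 1.0, 1.6, 2.2 and 2.9 mg/kg. Cohort sizes (Section 9.2 table): 1 in cohort 01; 3 + 3 conditional in cohorts 02 to 07. The plan states no target or expected DLT rate.

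**The plan's own figure.** Maximum N = 1 + 6 × (3 + 3) = 37, which matches the Synopsis. With no DLT at any dose, N = 1 + 6 × 3 = 19, of whom 3 receive 2.9 mg/kg.

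**Toxicity rate at the labelled dose.** 2/6 = 33%. The exact (Clopper-Pearson) 95% interval is 0.043 to 0.777.

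**Distance from the label to the highest dose cleared**, as stopping dose divided by the next lower dose:

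| Stop at cohort | Labelled MTD (mg/kg) | Highest dose cleared (mg/kg) | Ratio |
|---|---|---|---|
| 07 | 2.9 | 2.2 | 1.32 |
| 06 | 2.2 | 1.6 | 1.38 |
| 05 | 1.6 | 1.0 | 1.60 |
| 04 | 1.0 | 0.625 | 1.60 |
| 03 | 0.625 | 0.3 | 2.08 |
| 02 | 0.3 | none in a full cohort (0.06: 0/1) | not given |

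No ratio is given for cohort 02, because one sentinel volunteer does not establish a tolerated dose.

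**Outcomes at 2.9 mg/kg under the readable rules:**

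| DLTs at 2.9 mg/kg | What the readable rules say |
|---|---|
| 0/3 | Rule (a) points to a next cohort that does not exist; no MTD |
| 1/3, then 0/3 (1/6) | No rule applies; no MTD |
| 1/3, then 1/3 (2/6) | Rule (c): MTD = 2.9; Section 3 supported |
| 2 or 3 of the first 3, or 3 or more of 6 | Not literally covered |

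A 2/6 at a lower dose labels that lower dose and contradicts Section 3. On this text, support therefore requires DLTs at 2.9 mg/kg. A clean cohort 07 gives 0/3, with exact 95% interval 0 to 1 − 0.025^(1/3) = 0.708.

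**How often, if 2.9 mg/kg is reached.** The true DLT rate p is an assumption, shown over a range, with q = 1 − p. P(0/3 or 1/6) = q³ + 3pq² × q³. P(exactly 2/6) = (3pq²)².

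| p | No MTD assigned | 2.9 labelled MTD by 2/6 |
|---|---|---|
| 1% | 99.9% | 0.1% |
| 5% | 97.3% | 1.8% |
| 10% | 90.6% | 5.9% |
| 20% | 70.9% | 14.8% |
| 33% | 43.4% | 19.8% |

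Over this range, the better 2.9 mg/kg is tolerated, the less likely Section 3 is to be supported. For example, at p = 10%: 0.729 + 0.243 × 0.729 = 0.906, and 0.243² = 0.059.

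**The case against.** The strongest objection concerns Section 3. Figure 7, the escalation scheme, is not shown, and Section 1.5.2.2, on the maximum dose, is redacted. Either could say what follows from a clean cohort 07. A reader might infer that a well-tolerated top dose certainly leaves the hypothesis without a verdict, but the documents do not support that, so this part is conditional. Section 3 can also be read as a premise for choosing the top dose, since no readable part of Section 9 attaches a test to it, although its heading presents it as a hypothesis to be tested. The labelling point does not depend on either missing item, because all five statements of rule (c) are readable.

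It can also be said that Section 4.3.3 refers back to the design section, governs only the opening of the next cohort, and does not define tolerated. That is true. Even so, a dose that fails the protocol's only stated safety condition should not carry that word, and no readable text sets a target DLT rate at which 2/6 would be acceptable.

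Third, the practical effect is small. The MTD is not an objective or endpoint, and the proportion with grade 3-4 events is reported by cohort, so the 2/6 would appear alongside the label. This stands, and it limits the severity.

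Two further inferences go too far. One is that a stop at cohort 02 puts the label five times too high (0.3 against 0.06 mg/kg); that treats a single sentinel volunteer as having established an MTD. The other is that escalation could continue after two DLTs in the first three volunteers. No rule names that case, but rule (a) requires no DLTs, so nothing permits the next dose. It is a gap in the wording.

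**Conclusion.** Rule (c) is wrong as written and should be fixed. It gives the MTD label to a dose with 33% observed DLTs (exact 95% CI 4% to 78%). For stops at cohorts 03 to 07 this is 1.32 to 2.08 times the highest dose cleared, if 1/6 counts as cleared, which the readable text does not state. For a stop at cohort 02 no MTD could be established.

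The Section 3 point holds only if neither Figure 7 nor Section 1.5.2.2 supplies a rule for a cleared top dose. In that case 0/3 or 1/6 at 2.9 mg/kg yields no MTD, and only DLTs at that dose can support the hypothesis.

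Volunteers are not exposed to higher doses because of the label: escalation still stops at 2/6. The PK, PD and safety endpoints are unchanged. What is at risk is the reading of the result when the phase II dose range is set.

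**What to change.** In the Synopsis and Sections 1.5.1, 4.2, 4.4.1 and 6.1, replace rule (c) with wording such as: *Two or more volunteers with DLTs at a dose, whether among the first three or among six, stop escalation, and that dose is recorded as exceeding the MTD. The MTD is the highest lower dose cleared under the escalation rules (0/3, or 1/6 after expansion), reported as DLTs over volunteers treated with an exact 95% CI. If escalation stops at cohort 02, report: no MTD established (0.06 mg/kg: 0/1).*

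Stopping at two of the first three and counting 1/6 as cleared are clarifications of the decision rule, so check both against Figure 7 before adopting them.

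Unless Figure 7 or Section 1.5.2.2 already covers it, restate Section 3 as an estimation aim that allows the conclusion *MTD not reached; doses up to 2.9 mg/kg tolerated*, with its precision (for 0/3, exact 95% CI 0% to 71%). A clean cohort 07 need not be expanded.

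The cost is a protocol amendment and a more modest MTD statement. No volunteers are added, and the maximum N stays at 37.

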1.5.2. Justification of for the starting and maximum doses of BCD-089

1.5.2.1. Starting dose of BCD-089

According to the Guidelines for Conducting Preclinical Studies of Medicinal Products (part one)" (M.: FSBI "SCEEMP" of the Ministry of Health of Russia. - 2013, p. 854-864) for calculation of the maximum single starting dose (MSSD) for the first use of a novel drug in humans, it is necessary to determine the no-observed-adverse-effect level (NOAEL) in animals. The definition of NOAEL in the above guidelines says: "no-observed-adverse-effect level is the largest dose studied in animals, which does not cause a significant increase in **negative effects** compared to the control group. Negative effects that are biologically significant should be considered when determining NOAEL" (p. 855).

Translated from Russian to English, dated 06-Jul-2020

[Redacted content]

Translated from Russian to English, dated 06-Jul-2020

[REDACTED]

